16.11.8. Safety Figures

Safety: Figures					
No.	Population	IDSL / Example Shell	Title	Programming Notes	Deliverable [Priority]
Laboratory					
3.001	All Treated	LIVER14	Scatter Plot of Maximum vs. Baseline for ALT	Report for: Part 1, Part 2, and combined Part 1 and Part 2; Create plot per treatment group	P-SAC [3], F-SAC [4]
3.002	All Treated	LIVER9	Scatter Plot of Maximum Bilirubin vs. Maximum ALT – eDISH	Report for: Part 1, Part 2, and combined Part 1 and Part 2; Create plot per treatment group	P-SAC [3], F-SAC [4]
3.003	All Treated	LIVER9	Scatter Plot of Maximum AST vs Maximum LDH - eDISH Plot	Report for: Part 1, Part 2, and combined Part 1 and Part 2; Create plot per treatment group	P-SAC [3], F-SAC [4]
3.004	All Treated	LIVER9	Scatter Plot of Maximum AST vs Maximum Creatinine Kinase - eDISH Plot	Report for: Part 1, Part 2, and combined Part 1 and Part 2; Create plot per treatment group	P-SAC [3], F-SAC [4]
3.005	All Treated	LIVER9	Scatter Plot of Maximum LDH vs Maximum Creatinine Kinase - eDISH Plot	Report for: Part 1, Part 2, and combined Part 1 and Part 2; Create plot per treatment group	P-SAC [3], F-SAC [4]
3.006	All Treated	LIVER9	Scatter Plot of Maximum Albumin/Creatinine Ratio (> 2000 mg/g) vs. Concomitant Values of Serum Creatinine	Report for: Part 1, Part 2, and combined Part 1 and Part 2; Create plot per treatment group; Concomitant window = \pm 7 days; If more than 3 participants	P-SAC [3], F-SAC [4]
Exposure					
3.007	All Treated	OEX12	Plot of Duration of Study Treatment by Response	Report for: Part 1, Part 2, and combined Part 1 and Part 2; Add	P-SAC [3], F-SAC [4]

Safety: Figures					
No.	Population	IDSL / Example Shell	Title	Programming Notes	Deliverable [Priority]
				the following footnote: "Subject PPD PPD and PP are continuing to Post Analysis Continued Treatment (PACT)."	

Safety: Figures					
No.	Population	IDS / Example Shell	Title	Programming Notes	Deliverable [Priority]
ECG					
3.008	All Treated	OECG4	Fridericia's QTc Shifts from Baseline to Worst-case Post Baseline	Report for: Part 1, Part 2, and combined Part 1 and Part 2;	P-SAC [3], F-SAC [4]
Profile Plot					
3.009	All Treated	See programming notes	Profile Plot for Subjects	Report for: Part 1, Part 2, and combined Part 1 and Part 2; Refer to mid205678 (primary_01) Figure 3.0031 for guidance	P-SAC [3], F-SAC [4]

16.11.9. Pharmacokinetic Tables

Pharmacokinetic: Tables					
No.	Population	IDSL / Example Shell	Title	Programming Notes	Deliverable [Priority]
PK					
4.001	PK	PK01	Summary of Plasma GSK2857916 (ADC) Pharmacokinetic Concentration-Time Data (ng/mL)	Report for: Part 1, Part 2, and combined Part 1 and Part 2; Include the following footnote: Note: Samples collected as End of Infusion Pembrolizumab are included in the SOI + 2hr time point.	P-SAC [3], F-SAC [4]
4.002	PK	PK01	Summary of Plasma GSK2857916 (Total Antibody) Pharmacokinetic Concentration-Time Data (ng/mL)	Report for: Part 1, Part 2, and combined Part 1 and Part 2; Include the following footnote: Note: Samples collected as End of Infusion Pembrolizumab are included in the SOI + 2hr time point.	P-SAC [3], F-SAC [4]
4.003	PK	PK01	Summary of Plasma GSK2857916 (cys-mcMMAF) Pharmacokinetic Concentration-Time Data (pg/mL)	Report for: Part 1, Part 2, and combined Part 1 and Part 2; Include the following footnote: Note: Samples collected as End of Infusion Pembrolizumab are included in the SOI + 2hr time point.	P-SAC [3], F-SAC [4]

Pharmacokinetic: Tables					
No.	Population	IDSL / Example Shell	Title	Programming Notes	Deliverable [Priority]
4.004	PK	PK04	Summary of Derived Plasma GSK2857916 (ADC) Pharmacokinetic Parameters	
Report for: Part 1, Part 2, and combined Part 1 and Part 2; Report only Cycle 1 Day 1; Include the following footnotes:
 
Note: PK parameters labelled 'Cycle 1 Day 1' are based on the full first cycle duration.
 
Note: AUC(0-tau) represents AUC during Cycle 1.
	P-SAC [3]
4.005	PK	PK04	Summary of Derived Plasma GSK2857916 (Total Antibody) Pharmacokinetic Parameters	
Report for: Part 1, Part 2, and combined Part 1 and Part 2; Report only Cycle 1 Day 1; Include the following footnotes:
 
Note: PK parameters labelled 'Cycle 1 Day 1' are based on the full first cycle duration.
 
Note: AUC(0-tau) represents AUC during Cycle 1.
	P-SAC [3], F-SAC [4]

Pharmacokinetic: Tables					
No.	Population	IDSL / Example Shell	Title	Programming Notes	Deliverable [Priority]
4.006	PK	PK04	Summary of Derived Plasma GSK2857916 (cys-mcMMAF) Pharmacokinetic Parameters	Report for: Part 1, Part 2, and combined Part 1 and Part 2; Report only Cycle 1 Day 1; Include the following footnotes: Note: PK parameters labelled 'Cycle 1 Day 1' are based on the full first cycle duration.	P-SAC [3], F-SAC [4]
4.007	PK	PK13	Listing of Derived Plasma GSK2857916 (ADC) Pharmacokinetic Parameters (non-transformed)	Report for: Part 1 and Part 2; Include the following footnotes: Note: PK parameters labelled 'Cycle 1 Day 1' are based on the full first cycle duration. Note: AUC(0-tau) represents AUC during Cycle 1.	P-SAC [3]
4.008	PK	PK13	Listing of Derived Plasma GSK2857916 (Total Antibody) Pharmacokinetic Parameters (non-transformed)	Report for: Part 1 and Part 2; Include the following footnotes: Note: PK parameters labelled 'Cycle 1 Day 1' are based on the full first cycle duration. Note: AUC(0-tau) represents AUC during Cycle 1.	P-SAC [3], F-SAC [4]

CONFIDENTIAL

205207

Pharmacokinetic Tables					
No.	Population	IDSL / Example Shell	Title	Programming Notes	Deliverable [Priority]
4.009	PK	PK13	Listing of Derived Plasma GSK2857916 (cys-mcMMAF) Pharmacokinetic Parameters (non-transformed)	Report for: Part 1 and Part 2; Include the following footnotes: Note: PK parameters labelled 'Cycle 1 Day 1' are based on the full first cycle duration.	P-SAC [3], F-SAC [4]

16.11.10. Pharmacokinetic Figures

Pharmacokinetic Figures					
No.	Population	IDS / Example Shell	Title	Programming Notes	Deliverable [Priority]
PK					
4.001	PK	PK16a	Individual Plasma GSK2857916 (ADC) Concentration-Time Plots (Linear and Semi-log)	Report for: Part 1 and Part 2	P-SAC [3], F-SAC [4]
4.002	PK	PK16a	Individual Plasma GSK2857916 (Total Antibody) Concentration-Time Plots (Linear and Semi-log)	Report for: Part 1 and Part 2	P-SAC [3], F-SAC [4]
4.003	PK	PK16a	Individual Plasma GSK2857916 (cys-mcMMAF) Concentration-Time Plots (Linear and Semi-log)	Report for: Part 1 and Part 2	P-SAC [3], F-SAC [4]
4.004	PK	PK17	Cycle 1 Mean Plasma GSK2857916 (ADC) Concentration-Time Plots (Linear and Semi-log)	Report for: Part 1, Part 2, and combined Part 1 and Part 2;	P-SAC [3], F-SAC [4]
4.005	PK	PK17	Cycle 1 Mean Plasma GSK2857916 (Total Antibody) Concentration-Time Plots (Linear and Semi-log)	Report for: Part 1, Part 2, and combined Part 1 and Part 2;	P-SAC [3], F-SAC [4]
4.006	PK	PK17	Cycle 1 Mean Plasma GSK2857916 (cys-mcMMAF) Concentration-Time Plots (Linear and Semi-log)	Report for: Part 1, Part 2, and combined Part 1 and Part 2;	P-SAC [3], F-SAC [4]
4.007	PK	PK18	Cycle 1 Median Plasma GSK2857916 (ADC) Concentration-Time Plots (Linear and Semi-log)	Report for: Part 1, Part 2, and combined Part 1 and Part 2;	P-SAC [3], F-SAC [4]
4.008	PK	PK18	Cycle 1 Median Plasma GSK2857916 (Total Antibody) Concentration-Time Plots (Linear and Semi-log)	Report for: Part 1, Part 2, and combined Part 1 and Part 2;	P-SAC [3], F-SAC [4]
4.009	PK	PK18	Cycle 1 Median Plasma GSK2857916 (cys-mcMMAF) Concentration-Time Plots (Linear and Semi-log)	Report for: Part 1, Part 2, and combined Part 1 and Part 2;	P-SAC [3], F-SAC [4]

16.11.11. Biomarker Figures

Biomarker: Figures					
No.	Population	IDS / Example Shell	Title	Programming Notes	Deliverable [Priority]
sBCMA					
5.001	PD	BIO_F1	Absolute Free sBCMA Versus Cycle and Timepoint by Best Confirmed Response (Log Scale)	Report for: Part 1, Part 2, and combined Part 1 and Part 2; Categorize best overall response in the following: Response (subjects with PR or better), Non-Response (subjects with MR, SD, or PD) and NE (subjects with NE)	P-SAC [3], F-SAC [4]
5.002	PD	BIO_F1	Fold Change from Baseline in Free sBCMA Versus Cycle and Timepoint by Best Confirmed Response (Log Scale)	Report for: Part 1, Part 2, and combined Part 1 and Part 2; Categorize best overall response in the following: Response (subjects with PR or better), Non-Response (subjects with MR, SD, or PD) and NE (subjects with NE)	P-SAC [3], F-SAC [4]
5.003	PD	BIO_F2	Boxplot of Baseline sBCMA by Best Confirmed Response (Log Scale)	Report for: Part 1, Part 2, and combined Part 1 and Part 2; Categorize best overall response in the following: Response (subjects with PR or better), Non-Response (subjects with MR, SD, or PD) and NE (subjects with NE)	P-SAC [3], F-SAC [4]
5.004	PD	BIO_F3	Boxplot of Baseline sBCMA and Other Disease Burden Markers (e.g., β 2M, FLC, M-protein) Versus Best Confirmed Response and Extramedullary Disease (Log Scale)	Report for: Part 1, Part 2, and combined Part 1 and Part 2; Categorize best overall response in	P-SAC [3], F-SAC [4]

Biomarker: Figures					
No.	Population	IDSL / Example Shell	Title	Programming Notes	Deliverable [Priority]
				the following: Response (subjects with PR or better), Non-Response (subjects with MR, SD, or PD) and NE (subjects with NE); Categorize EMD in the following: EMD No (subjects without EMD), EMD Yes (subjects with EMD),	

16.11.12. Health Outcomes Tables

Health Outcomes: Tables					
No.	Population	IDSL / Example Shell	Title	Programming Notes	Deliverable [Priority]
PRO-CTCAE					
6.001	All Treated	See programming notes	Summary of Maximum Post-Baseline PRO-CTCAE Score	Report for: Part 1, Part 2, and combined Part 1 and Part 2; Summarize by: dose level (Refer to Section 5.1 for ordering of dose level and omit 1.92 mg/kg if data is not available) Refer to mid205678 (primary_01) Table 8.0090 for guidance. For each selected item from PRO-CTCAE library: create summary Table for maximum post-baseline PRO-CTCAE score for each of 3 attributes (frequency, severity and/or interference). Presence/Absence will only be listed.	P-SAC [3], F-SAC [4]
OSDI					
6.002	All Treated	See programming notes	Summary of Change in OSDI Subscale Scores from Baseline	Report for: Part 1, Part 2, and combined Part 1 and Part 2; Summarize by: dose level (Refer to Section 5.1 for ordering of dose level and omit 1.92 mg/kg if data is not available) Refer to mid205678 (primary_01) Table 8.00130 for guidance; Additional	P-SAC [3], F-SAC [4]

Health Outcomes: Tables					
No.	Population	IDSL / Example Shell	Title	Programming Notes	Deliverable [Priority]
				timepoints includes EOT visit, last follow-up visit, and worst change from baseline.	
6.003	All Treated	See programming notes	Summary of Subjects with a 12.5 Point or Greater Deterioration from Baseline in the OSDI Vision-Related Function Subscale Score	
Report for: Part 1, Part 2, and combined Part 1 and Part 2; Summarize by: dose level (Refer to Section 5.1 for ordering of dose level and omit 1.92 mg/kg if data is not available); Refer to mid205678 (present_2020_04) Table 8.0160 for guidance. Include the following footnotes:
 
(1) Improvement is defined as a decrease from the worst subscale score of at least 12.5 points.
 
(2) Time to 12.5 point deterioration assessed only for those subjects experiencing a first worsening of at least one 12.5 unit as compared to the baseline score with complete onset date.
 
(3) Time to improvement is defined as time from the onset of first worsening of at least one 12.5 unit as compared to the baseline score to the first time of resolution based on 12.5 improvement from the first worst subscale score during the event.
	P-SAC [3], F-SAC [4]

Health Outcomes: Tables					
No.	Population	IDS / Example Shell	Title	Programming Notes	Deliverable [Priority]
				It requires at least one day gap between the resolution of worsening from first course to the onset of second course.	
NEI-VFQ-25					
6.004	All Treated	See programming notes	Summary of Change in NEI-VFQ-25 Subscale Scores from Baseline	Report for: Part 1, Part 2, and combined Part 1 and Part 2; Summarize by: dose level (Refer to Section 5.1 for ordering of dose level and omit 1.92 mg/kg if data is not available). Refer to mid205678 (primary_01) Table 8.0110 for guidance. Including 11 subscale score. Additional timepoints includes EOT visit, last follow-up visit, and worst change from baseline; include both investigator and subject assessed data	P-SAC [3], F-SAC [4]
EORTC QLQ-C30					
6.005	All Treated	See programming notes	Summary of Change in EORTC QLQ-C30 Domain Scores from Baseline (Part 2)	Report for: Part 2; Refer to mid205678 (primary_01) Table 8.0020 for guidance. Including score for 15 domains and Improvement in EORTC QLQ-C30 domain score >=10	P-SAC [3], F-SAC [4]

Health Outcomes: Tables					
No.	Population	IDSL / Example Shell	Title	Programming Notes	Deliverable [Priority]
EORTC QLQ-MY20					
6.006	All Treated	See programming notes	Summary of Change in EORTC QLQ-MY20 Domain Scores from Baseline (Part 2)	Report for: Part 2; Refer to mid205678 (primary_01) Table 8.0070 for guidance. Including score for 4 domains and Improvement in EORTC QLQ-MY20 domain score >=10	P-SAC [3], F-SAC [4]
Compliance of PRO-CTCAE, OSDI, and EORTC QLQ-C30					
6.007	All Treated	See programming notes	Summary of Compliance of OSDI by Visit	Report for: Part 1, Part 2, and combined Part 1 and Part 2; Summarize by: dose level (Refer to Section 5.1 for ordering of dose level and omit 1.92 mg/kg if data is not available). Refer to mid205678 (primary_08) Table 8.10011 for guidance. Include number and percentage of subjects for each assessment. Footnote: Note: percentage is calculated using number of subject remaining in the study at given timepoint as denominator.	P-SAC [3], F-SAC [4]
6.008	All Treated	See programming notes	Summary of Compliance of EORTC QLQ-C30 and EORTC QLQ-MY20 by Visit (Part 2)	Report for: Part 2; Refer to mid205678 (primary_08) Table 8.10010 for guidance. Include number and percentage	P-SAC [3], F-SAC [4]

Health Outcomes: Tables					
No.	Population	IDSL / Example Shell	Title	Programming Notes	Deliverable [Priority]
				of subjects for each assessment. Footnote: Note: percentage is calculated using number of subject remaining in the study at given timepoint as denominator.	

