13. PATIENT REPORTED OUTCOMES ANALYSES

All questionnaires will be collected electronically as Electronic Patient Reported Outcomes (ePRO). The EORTC QLQ-C30 (version 3.0), EORTC QLQ-MY20, and the PRO-CTCAE are three oncology-specific Health-Related Quality-of-Life (HRQoL) assessments that will be analysed in this study.

In addition, the impact of potential corneal event on function and health-related quality-of-life will be assessed with the use of two visual function questionnaires, the NEI-VFQ-25 and Ocular Surface Disease Index (OSDI).

The analyses for EORTC QLQ-C30, EORTC QLQ-MY20, PRO-CTCAE, NEI-VFQ-25, and OSDI will be based on the All Treated population, unless otherwise specified.

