13.2.2. Ocular Surface Disease Index

The Ocular Surface Disease Index (OSDI) is a 12-item questionnaire designed to assess both the frequency of dry eye symptoms and their impact on vision-related functioning [Schiffman, 2000]. The OSDI has demonstrated good reliability, validity, sensitivity, and specificity, and can be used as a complement to other clinical and subjective measures of dry eye disease by providing a quantifiable assessment of dry eye symptom frequency and the impact of these symptoms on vision-related functioning.

For the OSDI, the total score will be calculated as well as scores for the three subscales (ocular symptom: item 1-3; vision-related function: item 4-9; and environmental triggers: item 10-12).

The total OSDI score = ([sum of scores for all questions answered \times 100]/[total number of questions answered \times 4]). Subscale scores are computed similarly with only the questions from each subscale used to generate its own score. Subscale scores are computed similarly with only the questions from each subscale used to generate its own score. A score of 100 corresponds to complete disability (a response of “all of the time” to all questions answered), while a score of 0 corresponds to no disability (a response of “none of the time” to all questions answered). Therefore, decrease in score from baseline means improvement.

For each of the three sub-scales, the descriptive summary of the actual value and change from baseline at selected time points will be provided. For the Vision-Related Functioning domain, the number and percentage of participants with post-baseline score worsening of ≥ 12.5 from baseline score will be summarized at selected time points. Additionally, a time to event analysis of time to meaningful worsening based on the ≥ 12.5 threshold will be summarized with frequency of number of patients with event (N, %). Time to first event and duration of event will also be calculated (median days, range). Additionally, recovery from first event defined as ≥ 12.5 decrease from the first worst score will be summarized.

Plots of mean change from baseline (including baseline) and 95% confidence interval over time by visit, and at end of study treatment, last follow-up, and worst case post-baseline for individual domains will also be provided. The overall total score and sub-scale scores will be listed.

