16.7.2. Handling of Missing Data

Element	Reporting Detail
General	
 Missing data occurs when any requested data is not provided, leading to blank fields on the collection instrument: 
 These data will be indicated by the use of a "blank" in subject listing displays. Unless all data for a specific visit are missing in which case the data is excluded from the Table. Answers such as "Not applicable" and "Not evaluable" are not considered to be missing data and should be displayed as such.
Outliers	
 Any participants excluded from the summaries and/or statistical analyses will be documented along with the reason for exclusion in the clinical study report.
Responder Analysis	
 For endpoints which determine the percentage of responders, subjects with unknown/not evaluable or missing best overall response will be assumed to be non-responders and will be included in the denominator when calculating the percentages.
Time to Event	
 Because study treatment is dependent on the study endpoints (e.g., progression, i.e. not a fixed treatment duration), the length of treatment for each subject will depend on the efficacy and toxicity of the treatment, so the duration of treatment will vary across subjects. Similarly, the duration of follow up will also vary. All available time-to-event data will be analysed using suitable statistical methods; subjects with shorter treatment and follow-up due to the natural history of their disease or medical necessities of the treatment of their disease will not be considered to have missing time-to-event data.

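### The OSDI time-to-worsening median is computed only in subjects who worsened, so it is not an estimate of time to worsening in treated subjects

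*SAP*

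**What the plan says.** SAP Section 13.2.2 plans "a time to event analysis of time to meaningful worsening based on the ≥ 12.5 threshold" for the OSDI vision-related functioning domain. The output is the number and percentage of patients with an event, followed by a second sentence: "Time to first event and duration of event will also be calculated (median days, range"). No censoring rule and no Kaplan-Meier estimate are given.

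Section 13 sets the population: "OSDI will be based on the All Treated population, unless otherwise specified". Table 6.003 in Section 16.11.12 also lists All Treated, and is reported for Part 1, Part 2 and both combined, by dose level. Its footnote (2) then fixes who enters the time calculation: "Time to 12.5 point deterioration assessed only for those subjects experiencing a first worsening of at least one 12.5 unit". The same footnote adds a second restriction: "as compared to the baseline score with complete onset date".

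The general rule for time-to-event data in Section 16.7.2 notes that follow-up will differ between subjects, and continues: "All available time-to-event data will be analysed using suitable statistical methods". Appendix 11 lists no Kaplan-Meier table or figure for OSDI.

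**The concern.** A time-to-event analysis uses the event-free follow-up of subjects who have not had the event. Footnote (2) removes that information. Subjects who never worsened, or who stopped completing the questionnaire before worsening, add nothing to the time calculation, so the analysis is selected on its own outcome. It answers how early the worsening came in those who worsened, not how long a treated patient goes before worsening.

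OSDI is one of the two visual function questionnaires in the study, and corneal events and eye disorders are adverse events of special interest for belantamab mafodotin. Table 6.003 sets results side by side by dose level and part. Where follow-up or the share with events differs between columns, the medians differ for reasons unrelated to how fast patients worsen.

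**Working it through.** The SAP states no worsening rate, sample size or precision for this analysis, so there is no planned figure to reproduce. The direction of the error follows from the definition. Its size needs assumptions.

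**Direction.** Let F be the distribution of time to worsening, τ a common follow-up, and p = F(τ) the share who worsen by τ. The median among subjects with the event is the time by which half of p have worsened, i.e. the p/2 quantile of F. The true median is the 0.5 quantile. Since p/2 < 0.5 whenever p < 1, the events-only median comes out short whatever the shape of the hazard.

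**Size, closed form.** Assume a constant hazard, λ = −ln(1−p)/τ. Then:

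- events-only median / τ = ln(1−p/2) / ln(1−p)
- true median / τ = ln(0.5) / ln(1−p)

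| Share worsened by τ | Events-only median / τ | True median / τ | Shortfall |
|---|---|---|---|
| 30% | ln 0.85 / ln 0.70 = 0.46 | 1.94, not reached | – |
| 50% | ln 0.75 / ln 0.50 = 0.42 | 1.00 | 58% |
| 70% | ln 0.65 / ln 0.30 = 0.36 | 0.58 | 38% |
| 80% | ln 0.60 / ln 0.20 = 0.32 | 0.43 | 26% |
| 90% | ln 0.55 / ln 0.10 = 0.26 | 0.30 | 14% |

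With τ = 365 days, the events-only median runs from 172 days (20% worsened) to 95 days (90% worsened). The true median runs from 1134 to 110 days.

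**Dependence on follow-up.** A simulation used 28 subjects (the Part 2 maximum in Section 3.1.2.1), exponential worsening and dropout, follow-up capped at 730 days, and 3000 runs per scenario. The worsening and dropout rates are assumed. With the true median held at 240 days:

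| Median follow-up (days) | Kaplan-Meier median | Events-only median |
|---|---|---|
| 90 | 257 (not reached in 27% of runs) | 66 |
| 180 | 242 | 102 |
| 365 | 239 | 140 |

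The events-only figure more than doubles (140/66 = 2.1) with no change in the true rate. Conversely, with median follow-up held at 180 days and true medians of 120, 240 and 480 days, the events-only medians are 73, 102 and 128 days. A fourfold true range shrinks to 128/73 = 1.75-fold.

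**Against the SAP's own practice.** Section 7.2.2.2 uses Kaplan-Meier for DoR, PFS, OS and TTP. Section 13.2.2 does not define the OSDI time as conditional on worsening. That condition appears only in the table footnote.

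**The case against.** The case on the other side has real substance.

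- Section 13.2.2 states its own output: a count and percentage, then a median and range. On that reading no censored analysis was promised, and footnote (2) openly says who is in the median. This stands as to disclosure. It does not make the output the analysis that the section names.
- Onset summaries restricted to subjects with the event are used elsewhere: adverse events of special interest (8.2.1.1), visual acuity worsening (8.5), and time to response (7.2.2.2). That is correct, so the SAP has no uniform Kaplan-Meier convention. But time to response is conditional on response by definition, and the safety onset summaries are not called time-to-event analyses.
- The endpoint is exploratory in a single-arm study, with no OSDI test and no decision rule attached. This stands and limits the consequence.
- Part 1 has about 12 subjects in total, so Kaplan-Meier medians by dose level would be imprecise. This also stands.

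Three stronger readings are tempting and not supported. A reader might infer that event-free subjects vanish from the OSDI reporting. They do not: they remain in the number and percentage with an event, the by-visit percentages, the change-from-baseline table and plots, and the listing. A reader might infer that the median is meaningless. It is a valid description of timing among those who worsened. A reader might infer that it is always short by a quarter or more, or hardly responds to the true rate. At 90% worsening the shortfall is about 14%, and at fixed follow-up of 365 days the figure does move, from 172 to 95 days.

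**Conclusion.** The point holds. Section 13.2.2 names a time-to-event analysis, and Table 6.003 delivers onset time among subjects with the event and a complete onset date. Taken as time to worsening in treated subjects, the median is biased short whenever some subjects stay event-free, and it depends strongly on length of follow-up.

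The size is illustrative. Under a constant hazard and common follow-up, the shortfall is 58% when half the subjects worsen and about 14% when 90% do. At 30% a median is reported although the true one is not reached. These figures rest on assumed rates and follow-up that the SAP does not supply. The direction rests on less: some subjects event-free, and follow-up unrelated to worsening.

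The primary ORR conclusion is not affected. The change should be made because it is cheap and concerns a patient-reported measure of ocular tolerability.

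**What to change.** In Section 13.2.2 and Table 6.003, footnote (2):

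- Estimate time to first worsening of at least 12.5 points by Kaplan-Meier in All Treated subjects with a baseline and at least one post-baseline OSDI score.
- Censor event-free subjects at their last OSDI assessment.
- State how death before worsening is handled: censored, or as a competing event with cumulative incidence.
- Report the median and quartiles with Brookmeyer-Crowley 95% confidence intervals, as Section 7.2.2.2 does for PFS and OS.
- Keep the present median and range as a descriptive row labelled *time to onset among subjects with worsening*.

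The cost is SAP wording and one further analysis on data already collected. The downside is that the median may be not reached, and will be imprecise in the small dose groups. Censoring at the last questionnaire also assumes that stopping completion is unrelated to worsening, which the report should say. If the sponsor does not want the added analysis, the minimum is to stop calling the present output a time-to-event analysis and to use the descriptive label.
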